19.3.2. SEL-110 Instructions

Follow instructions below:

1. Convert weight of subject to kg, as needed (weight in pounds divided by 2.2046).
2. Calculate the volume (mL) of SEL-110 required for a subject, with a maximum volume of 6.0 mL (equivalent to 12 mg of rapamycin in SEL-110) per study visit per individual in cohorts receiving SEL-110 doses <0.10 mg/kg. If calculated required dose volume exceeds 6.0 mL, dose volume should be set to 6.0 mL. In cohorts receiving SEL-110 ≥ 0.10 mg/kg, there is no maximum volume of SEL-110, however their initial rate of SEL-110 is restricted to 5.5 mL/hr as described in section 9.5. If calculated required dose volume exceeds 6.0 mL, for cohorts receiving SEL-110 ≥ 0.10 mg/kg, the full calculated dose volume should be used.

$$\text{Volume (mL) SEL-110 required} = (\text{dose in mg/kg}) \times (\text{subject weight in kg}) / (\text{concentration of SEL-110 per ml in vial i.e., 2 mg/mL})$$

3. Calculate the number of vials of SEL-110 required for a subject. Round the calculation up to the next whole number.

$$\text{Number of SEL-110 vials required} = [\text{Volume (mL) SEL-110 required} + \text{priming volume (mL)}] / (5 \text{ mL/vial})$$

4. Thaw the required number of vials at room temperature for at least 2 hours. Once the vials are thawed, invert slowly (don't shake) each vial twenty times to ensure product is uniform. Do not use any vials with visible clumping. Thawed SEL-110 should be administered as soon as possible but thawed SEL-110 is stable at room temperature and normal light conditions for 24 hours.
5. Load a syringe with the appropriate size for the dose. In order to prime the line between the syringe and the injection site valve, an additional priming volume of SEL-110 (approximately 1.5mL), equal to the volume of the connecting line used (approximately 0.65mL) and the prime volume of the 5 micrometer membrane filter (Pall Medical, PN HP1050; 0.85 mL) used, should be added to the syringe. When loading syringes, do not bubble air through the product to avoid the formation of foam.
6. Start an infusion of 125 mL of normal saline solution over 60 minutes using an IV set with an injection site valve.
7. Start an infusion of SEL-110 as described below concurrently with the saline infusion of Step 6:
 - a) For cohorts receiving SEL-110 doses <0.1 mg/kg, using the injection site valve, immediately after starting the normal saline IV, slowly inject the SEL-110 using a syringe infusion pump at a single steady rate to deliver the dose over a period of 55 minutes. A 5 μ m syringe filter (5 μ m syringe filter Supor (PES) membrane, Pall Medical P/N HP1050) for single use must be included in the SEL-110 line downstream of the syringe and proximal to the injection site valve.
 - b) For cohorts receiving SEL-110 doses ≥ 0.1 mg/kg, using the injection site valve, immediately after starting the normal saline IV, slowly inject the SEL-110 using a syringe

Study: SEL-212/201 Version: 7.1	Effective Date March 19, 2018
------------------------------------	----------------------------------

infusion pump at an initial infusion rate equal to 5.5 mL/hour for the first 30 minutes of infusion and, then, change to a steady rate sufficient to deliver the remainder of the dose volume for the additional 25 minutes. A 5 µm syringe filter (5 µm syringe filter Supor (PES) membrane, Pall Medical P/N HP1050) for single use must be included in the SEL-110 line downstream of the syringe and proximal to the injection site valve.

At the end of the 55 minutes, continue the saline infusion for the additional 5 minutes after the SEL-110 infusion stops to flush the main line. Do not flush the line between the syringe and the injection site valve.

Example for subject weighing 200 pounds in Cohort _5_ (0.08 mg/kg group)

Step 1: If not already done convert weight to kg:

$$= 200 \text{ pounds} / 2.20462 = 90.7 \text{ kg}$$

Step 2: Calculate volume of SEL-110 needed, with a maximum volume of 6.0 mL

(equivalent to 12 mg of rapamycin in SEL-110) per study visit per individual, since the example cohort 5 is receiving <0.1 mg/kg SEL-110. If calculated required dose volume exceeds 6.0 mL, dose volume should be set to 6.0 mL:

$$= (0.08 \text{ mg/kg}) \times (90.7 \text{ kg}) / (2 \text{ mg/mL})$$

$$= 7.26/2 = 3.6 \text{ mL SEL-110}$$

Step 3: Calculate number of vials needed (assumes 1.5 mL prime volume):

$$= [3.6 \text{ mL SEL-110 required} + 1.5 \text{ mL}] / (5 \text{ mL/vial})$$

$$= 1.02 \text{ vials. Round up to 2 vials.}$$

Step 4 and 5: Thaw 2 vials and load syringe with 3.6 mL SEL-110 plus the priming volume (approximately 1.5 mL).

Step 6: Start infusion of 125 mL of normal saline solution over 60 minutes.

Step 7: Immediately after the start of the normal saline infusion, slowly inject 3.6 mL of SEL-110 at a single steady rate over 55 minutes, using a 5 µm syringe filter proximal to the injection site valve. At the end of the 55 minutes, continue the saline infusion for the additional 5 minutes after the SEL-110 infusion stops to flush the main line.

19.4. Laboratory Schedules by Cohort

Table 9: Laboratory Schedule - Cohorts 1 & 2 (SEL-037)

Labs for SEL-037 Cohorts 1&2		Treatment 1-5				EOS / Early Termination
Labs	screen	predose	D7	D14	D21	D30
Safety labs						
Alkaline phosphatase	x	x		x		x
ALT	x	x		x		x
APTT	x	x				x
AST	x	x		x		x
Electrolytes	x	x				x
Total Bilirubin	x	x				x
BUN	x	x				x
Calcium	x					
Total Complement ²	x					
Creatinine	x	x				x
eGFR	x					
Fibrinogen ¹	x	x				
Glucose(fasting)	x	x		x		x
Hct	x	x				x
Hgb	x	x				x
HbA1c	x					
Hep C Ab	x					
HIV 1/2	x					
INR	x	x				x
Phosphorous	x					
CBC with platelets	x	x		x		x
WBC c diff	x	x		x		x
Lipid Panel						
total cholesterol	x	x				x
HDL	x	x				x
LDL	x	x				x
Triglycerides	x	x				x
Urinalysis	x					
G6PD	x					
Immunogenicity						
Anti-Pegsiticase		x	x	x	x	x
Anti-Uricase		x	x	x	x	x
Anti-PEG	x	x	x	x	x	x
PK/PD						
SEL-110 PK						
SEL-037 PK		x ²	x	x	x	x
Uricase Activity		x ³	x	x	x	x
Uric Acid	x	x ²	x	x	x	x

¹ Collected at screening, results not required to determine eligibility

² Additional samples collected during D0 and D1 as per Schedule of Events timing

³ Additional sample collected D1 as per Schedule of Events timing

Table 10: Laboratory Schedule - Cohorts 3-8, 10, 11, and 12 (SEL-212)

Labs for SEL-212 Cohorts 3-8, 10, 11, & 12		Treatment Period 1-3				Treatment Period 4-5				EOS / Early Termination
Labs	screen	predose	D7	D14	D21	predose	D7	D14	D21	D30
Safety labs										
Alkaline phosphatase	x	x		x		x		x		x
ALT	x	x		x		x		x		x
APTT	x	x				x				x
AST	x	x		x		x		x		x
Electrolytes	x	x				x				x
Total Bilirubin	x	x				x				x
BUN	x	x				x				x
Calcium	x									
Total Complement ¹	x									
Creatinine	x	x				x				x
eGFR	x									
Fibrinogen ¹	x	x		x		x				
Glucose(fasting)	x	x	x	x	x	x		x		x
Hct	x	x	x	x	x	x				x
Hgb	x	x	x	x	x	x				x
HbA1c	x									
Hep C Ab	x									
HIV 1/2	x									
INR	x	x				x				x
Phosphorous	x	x	x	x	x	x		x		x
CBC with platelets	x	x	x	x	x	x	x	x	x	x
WBC c diff	x	x	x	x	x	x	x	x	x	x
Lipid Panel										
total cholesterol	x	x	x	x	x	x		x		x
HDL	x	x	x	x	x	x		x		x
LDL	x	x	x	x	x	x		x		x
Triglycerides	x	x	x	x	x	x		x		x
Urinalysis	x									
G6PD	x									
Immunogenicity										
Anti-Pegsiticase		x	x	x	x	x	x	x	x	x
Anti-Uricase		x	x	x	x	x	x	x	x	x
Anti-PEG	x	x	x	x	x	x	x	x	x	x
PK/PD										
SEL-110 PK		x ²	x	x	x	x ⁴				x
SEL-037 PK		x ²	x	x	x	x ²	x	x	x	x
Uricase Activity		x ³	x	x	x	x ³	x	x	x	x
Uric Acid	x	x ²	x	x	x	x ²	x	x	x	x
Exploratory										
Inflammatory markers		x ⁵								x
T-cell recall		x ⁵	x ⁶				x ⁷			x

¹ Collected at screening, results not required to determine eligibility

² Additional samples collected during D0 and D1 as per Schedule of Events timing

³ Additional sample collected D1 as per Schedule of Events timing

⁴ Predose sample only collected on Treatment Period 4 only

⁵ Predose sample only collected on Treatment Period 1 (Visit 4) only

⁶ Sample collected on Treatment Period 3 (Visit 18) only

⁷ Sample collected on Treatment Period 5 (Visit 30) only

Note: Cohort 9 is intentionally omitted from this protocol in order to maintain the cohort numbering convention of associating even numbered cohorts with the 0.4 mg/kg SEL-037 dose.

Table 11 Laboratory Schedule – Part C: Cohorts 13, 15, and 17 (SEL-212)

Labs for SEL-212		Treatment Period 1-5				EOS / Early Termination
Labs	Screen	Predose	D7	D14	D21	D30
Safety labs						
Alkaline phosphatase	x	x		x		x
ALT	x	x		x		x
APTT	x	x				x
AST	x	x		x		x
Electrolytes	x	x				x
Total Bilirubin	x	x				x
BUN	x	x				x
Calcium	x					
Total Complement ¹	x					
Creatinine	x	x				x
eGFR	x					
Fibrinogen ¹	x	x		x		
Glucose(fasting)	x	x	x	x	x	x
Hct	x	x	x	x	x	x
Hgb	x	x	x	x	x	x
HbA1c	x					
Hep C Ab	x					
HIV 1/2	x					
INR	x	x				x
Phosphorous	x	x	x	x	x	x
CBC with platelets	x	x	x	x	x	x
WBC c diff	x	x	x	x	x	x
Lipid Panel						
total cholesterol	x	x	x	x	x	x
HDL	x	x	x	x	x	x
LDL	x	x	x	x	x	x
Triglycerides	x	x	x	x	x	x
Urinalysis	x					
G6PD	x					
Immunogenicity						
Anti-Pegsiticase		x	x	x	x	x
Anti-Uricase		x	x	x	x	x
Anti-PEG	x	x	x	x	x	x
PK/PD						
SEL-110 PK		x ²	x	x	x	x
SEL-037 PK		x ³	x	x	x	x
Uricase Activity		x ²	x	x	x	x
Uric Acid ⁷	x	x ²	x	x	x	x
Exploratory						
Inflammatory markers		x	x			x
T-cell recall		x ⁵	x ⁶			x

¹ Collected at screening, results not required to determine eligibility

² Additional samples collected during D0 and D1 as per Schedule of Events timing

³ Additional sample collected D1 as per Schedule of Events timing

⁴ Predose sample only collected on Treatment Period 4 only

⁵ Predose sample only collected on Treatment Period 1 (Visit 4) only

⁶ Sample collected on Treatment Period 3 (Visit 18) and Treatment Period 5 (Visit 30) only

⁷ Collect 2 blood samples at each timepoint for sUA measurement. Store and ship 1 sample at ambient temperature and 1 sample under frozen conditions. Refer to the Laboratory Manual for details about sample handling.

Note: Cohorts 14 and 16 are intentionally omitted from this protocol in order to maintain the cohort numbering convention of associating odd numbered cohorts with the 0.2 mg/kg SEL-037 dose.

Table 12. Laboratory Schedule for Suspected Infusion Reaction, All Cohorts

Phases: Cohorts 1,2, 3-8, 10, 11, 12, 13, 15, & 17											
Hour (h)	At Event	Post event (time after suspected IR ^a)									
		0.25h	0.5h	0.75h	1h	1.5h	2h	3h	6h	12h	24h
Safety Labs											
Safety Labs - As indicated for predose in individual schedules	X										
Tryptase (total serum)	X		X				X		X		X
Histamine (plasma)	X	X					X				
Anti-Pegsiticase	X										
Anti-Uricase	X										
Anti-PEG	X										

^a All times are ± 5 minutes from suspected IR

Note: Cohort 9 is intentionally omitted from this protocol in order to maintain the cohort numbering convention of associating even numbered cohorts with the 0.4 mg/kg SEL-037 dose. Cohorts 14 and 16 are intentionally omitted from this protocol in order to maintain the cohort numbering convention of associating odd numbered cohorts with the 0.2 mg/kg SEL-037 dose.

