Uricase Activity	X			X		X	X	X	X	X	X	X	X	X	X	X	X
Uric Acid	X			X		X	X	X	X	X	X	X	X	X	X	X	X
Study Treatment	Pre-dose	0h	0.25h	0.5h	0.75h	1h	1.5h	2h	3h	6h	9h						
Study drug IV (SEL-037) : 0-60min			IV SEL-037														
Premedicate against Gout Flare ⁵																	
Premedicate against infusion reaction ⁶	X(-12h)	X(-2h)															
Premedicate against infusion reaction ⁷	X(-1h)																

1 - Confirm no active vaccinations
2 - Blood pressure after sitting 5 minutes, heart rate, oral temperature, respiratory rate
3 - If a conflict occurs due to multiple assessments occurring at the same time point, the ECG may be performed +/- 30 minutes from the designated time
4 - All Safety Labs indicated in individual schedule by cohort
5 - Premedicate with colchicine 0.6 mg QD beginning at D-7 for duration of study
6 - Premedicate with fexofenadine at -12h ± 2h and -2h ± 1h prior to dose
7 - Additionally premedicate with IV methylprednisolone at -1h ± 0.5h
8 - Window for visit is +/- 1 day
9 - Blood work as subset of listed points per schedules in Appendices by cohort
10 - DECT and Inflammatory markers at EOS unless done at previous P5 visit
11 - T-Cell recall sample ONLY for Treatment Period 5 (Visit 30) only

Study: SEL-212/201 Version: 7.1	Effective Date March 19, 2018
------------------------------------	----------------------------------

Table 3: Schedule of Events, Cohorts 3-8, 10, 11, and 12, Part A - Treatment Periods 1-3

Cohorts 3 - 8, 10, 11, & 12	Phases:	Screen	Outpatient Visits			In Clinic									Outpatient Follow-up Visits						
			V1 D-45 to -1	V2 ¹¹ P1 D-7	V3 P1 D-1	V4									V5 P1 D1	V6 P1 D7	V7 P1 D14	V8 P1 D21	Early Term		
Treatment Period #1; Visit (V); Day (D); Period (P)					V10									V11 P2 D1	V12 P2 D7	V13 P2 D14	V14 P2 D21	Early Term			
Treatment Period #2; Visit (V); Day (D); Period (P)					V16									V17 P3 D1	V18 P3 D7	V19 P3 D14	V20 P3 D21		Early Term		
Treatment Period #3; Visit (V); Day (D); Period (P)					V16									V17 P3 D1	V18 P3 D7	V19 P3 D14	V20 P3 D21	Early Term			
Hour (h)					Pre-dose	Infusion (time after dosing started)				Post-infusion (time after dosing started)				PK at ±2h from D0 0h ⁹	PK blood draws should occur at same time each visit ± 8 h from D0 0 hour ⁹						
						0h	0.25h	0.5h	0.75h	1h	1.5h	2h	3h	6h	9h						
Informed Consent		X																			
Dual Energy CT Scan		X																	X ¹⁵	X	
Inflammatory Markers					X ¹²															X	
T-Cell Recall					X ¹²												X ¹³			X	

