Demographics		X																			
Inclusion/exclusion		X		X																	
Medical History ¹		X		X																	
Safety Examinations					Pre-dose	0h	0.25h	0.5h	0.75h	1h	1.5h	2h	3h	6h	9h						
Physical Examination		X																		X	
Concomitant medications						continuous															
Vital signs ²		X			X	X	X	X	X	X	X	X	X	X	X	X	X	X	X	X	
Weight		X																	X		
ECG ³		X			X									X ¹⁰						X	
Adverse Events - Rheumatology CTC						continuous															
Safety Labs					Pre-dose	0h	0.25h	0.5h	0.75h	1h	1.5h	2h	3h	6h	9h						
Safety Labs - As indicated in individual schedules ⁴		X			X												X	X	X	X	
Immunogenicity																	X	X	X	X	
Anti-Pegsitticase					X												X	X	X	X	
Anti-Uricase					X												X	X	X	X	
Anti-PEG		X			X												X	X	X	X	
PK/PD Assessments																					
SEL-110 PK					X	X	X	X	X	X	X	X	X	X	X	X	X	X	X	X	
SEL-037 PK					X												X	X	X	X	
Uricase Activity					X				X	X	X	X	X	X	X	X	X	X	X	X	
Uric Acid		X			X				X	X	X	X	X	X	X	X	X	X	X	X	
Study Treatment					Pre-dose	0h	0.25h	0.5h	0.75h	1h	1.5h	2h	3h	6h	9h						
Study drug IV (SEL-110) : 0-55min ¹⁴						IV SEL-110															
Study drug IV (SEL-037) : 60-120 min										IV SEL-037											
Premedicate against Gout Flare ⁵			X																		
Premedicate against infusion reaction ⁶				X(-12h)	X(-2h)																
Premedicate against infusion reaction ⁷					X(-1h)																

- 1 - Confirm no active vaccinations
- 2 - Blood pressure after sitting 5 minutes, heart rate, oral temperature, respiratory rate
- 3 - If a conflict occurs due to multiple assessments occurring at the same time point, the ECG may be performed +/- 30 minutes from the designated time
- 4 - All Safety Labs indicated in individual schedule by cohort
- 5 - Premedicate with colchicine 0.6 mg QD beginning at D-7 for duration of study
- 6 - Premedicate with fexofenadine at -12h ± 2h and -2h ± 1h prior to dose
- 7 - Additionally premedicate with IV methylprednisolone at -1h ± 0.5h
- 8 - Window for visit is +/- 1 day
- 9 - Blood work as subset of listed points per schedules in Appendices by cohort
- 10 - ECG at 6 hr ONLY for Treatment Period 1, not for Treatment Periods 2 nor 3
- 11 - Gout flare premedication can be started during screening interval and does not require an on-site visit
- 12 - T-Cell recall sample and Inflammatory marker sample ONLY for Treatment Period 1 (Visit 4) only
- 13 - T-Cell recall sample ONLY for Treatment Period 3 (Visit 18) only

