10.3. Pharmacokinetic Assessments

The following PK parameters will be calculated on SEL-037, uricase activity and SEL-110 and assessed: the maximum observed serum concentration (C_{max}), the time at which C_{max} occurred (T_{max}), area under the serum concentration-time curve from time 0 to the time of last quantifiable concentration (AUC_{last}), area under the serum concentration-time curve from time 0 to infinity

(AUC_{inf}), the terminal elimination rate constant (K_{el}), terminal half-life ($t_{1/2}$), serum clearance of drug (CL), and apparent volume of distribution at equilibrium (V_{ss}).

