4. ENDPOINTS

4.1. PHARMACOKINETIC ENDPOINTS

The following PK parameters will be calculated on SEL-037 and SEL-110 (rapamycin) PK concentration as well as uricase activity separately for each analyte and type of PK assessment using noncompartmental intravascular infusion log-linear model for each Cohort and Treatment Period where possible and summarized statistically:

C_{max}	Maximum observed PK concentration or activity
T_{max}	Time of maximum observed PK concentration or activity
C_{last}	Last observed PK concentration or activity
T_{llast}	Time of last observed PK concentration or activity
AUC_{0-last}	Area under the serum concentration-time curve from time zero to the time of the last quantifiable PK concentration or activity
AUC_{0-inf}	Area under the PK concentration or activity-time curve from time zero extrapolated to infinity
$t_{1/2}$	Terminal elimination half-life
λ_z	Terminal elimination rate constant
CL	Clearance of drug
V_d	Terminal volume of distribution

Additional PK parameters may be calculated as needed. Change from baseline in uricase activity may be used for derivation of PK parameters in addition to actual measured activity.

Multiple dose parameters will be also derived where possible:

C_{min}	Min observed trough PK concentration or activity
T_{min}	Time of min observed PK concentration or activity
C_{ave}	Average observed PK concentration or activity
AUC_{τ}	Area under the PK concentration or activity from time 0 to the end of dosing interval
% Fluctuation	Difference between C_{max} and C_{min} normalized by average concentration
$R_{AUC\tau}$	Accumulation ratio based on comparison of AUC_{τ} between last and first dose
$R_{C_{max}}$	Accumulation ratio based on comparison of C_{max} between last and first dose
$R_{C_{min}}$	Accumulation ratio based on comparison of C_{min} between last and first dose
CL_{ss}	Steady state clearance (if steady state is achieved)

Statistical Analysis Plan

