8.1. COLLECTION SCHEDULE

Cohorts 1-2

Period	Day	Time from start of dose for saline, h	Time from start of dose for SEL-037, h	
			SEL-037 PK concentration	Uricase activity
1-3	0	0	-1 (0)	-1 (0)
		1.5		0.5
		2		1
		3		2
		6		5
		9		8
		1	23	23
		7	167	167
		14	336	335
	21	504	503	
	28*	672	671	
4-5	0		0	0
			0.5	0.5
			1	1
			1.5	1.5
			2	2
			3	3
			6	6
		1	24	24
		7	168	168
		14	336	336
	21	504	504	
28**	672	672		
30***		720	720	

* - pre-dose for next Treatment period

** - PK point for Treatment period 4 as pre-dose for Treatment period 5

*** - last point for Treatment period 5 only

Repeat the same for other periods

Statistical Analysis Plan

Cohorts 3-8, 10, 11, 12

Period	Day	Time from start of dose for SEL-110, h	Time from start of dose for SEL-037, h	
		SEL-110 concentration	SEL-037 PK concentration	Uricase activity
1-3	0	0	-1 (0)	-1 (0)
		0.25		
		0.5		
		0.75		
		1.5	0.5	
		2	1	
		3	2	
		6	5	
		9	8	
	1	23	23	
	7	167	167	
	14	336	335	
	21	504	503	
	28*	672	671	
4-5	0		0	
			0.5	
			1	
			1.5	
			2	
			3	
	1	6	24	24
	7	168	168	168
	14	336	336	336
	21	504	504	504
28**	672	672	672	
30***	720	720	720	

* - pre-dose for next Treatment period

** - PK point for Treatment period 4 as pre-dose for Treatment period 5

*** - last point for Treatment period 5 only

Statistical Analysis Plan

Cohorts 13, 15, 17

Period	Day	Time from start of dose for SEL-110, h	Time from start of dose for SEL-037, h	
		SEL-110 concentration	SEL-037 PK concentration	Uricase activity
1-5	0	0	-1 (0)	-1 (0)
		0.25		
		0.5		
		0.75		
		1.5	0.5	
		2	1	
		3	2	
		6	5	
		9	8	
		1	23	23
		7	167	167
14	336	335		
21	504	503		
28*	672	671		
30**		720		

* - pre-dose for next Treatment period

** - last point for Treatment period 5 only

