8.2. PHARMACOKINETIC PARAMETERS

The following PK parameters will be calculated on SEL-037 and SEL-110 (rapamycin) PK concentration as well as uricase activity using noncompartmental intravascular infusion log-linear model for each Cohort and Treatment Period where possible and summarized statistically:

C_{max}	Maximum observed PK concentration or activity
T_{max}	Time of maximum observed PK concentration or activity
C_{last}	Last observed PK concentration or activity
T_{last}	Time of last observed PK concentration or activity
AUC_{0-last}	Area under the serum concentration-time curve from time zero to the time of the last quantifiable PK concentration or activity
AUC_{0-inf}	Area under the PK concentration or activity-time curve from time zero extrapolated to infinity
$t_{1/2}$	Terminal elimination half-life
λ_z	Terminal elimination rate constant
CL	Clearance of drug
V_d	Terminal volume of distribution

Statistical Analysis Plan

Additional PK parameters may be calculated as needed.

Multiple dose parameters will be also derived where possible:

C_{min}	Min observed trough PK concentration or activity
T_{min}	Time of min observed PK concentration or activity
C_{ave}	Average observed PK concentration or activity
AUC_{tau}	Area under the PK concentration or activity from time 0 to the end of dosing interval
% Fluctuation	Difference between C_{max} and C_{min} normalized by average concentration
R_{AUCtau}	Accumulation ratio based on comparison of AUC_{tau} between last and first dose
R_{Cmax}	Accumulation ratio based on comparison of C_{max} between last and first dose
R_{Cmin}	Accumulation ratio based on comparison of C_{min} between last and first dose
CL_{ss}	Steady state clearance (if steady state is achieved)

Dose dependent parameters for SEL-110 (C_{max} , AUC_{0-last} , AUC_{0-inf}) will be dose normalized for comparison between treatments involving different doses of SEL-037.

The PK parameters will be estimated as follows:

The apparent C_{max} and the corresponding T_{max} will be read directly from the concentration-time plot (observed data, not predicted data by the program);

AUCs will be calculated using the linear-log trapezoidal rule;

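### Protocol tables disagree on whether SEL-037 concentration or uricase activity is sampled on Day 0, yet Cmax, Tmax, AUC and CL are derived for both

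*Protocol*

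**What the plan says.** Set side by side, the sampling instructions after the SEL-037 infusion on Day 0 are:

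| Source | Cohorts | SEL-037 concentration | Uricase activity |
|---|---|---|---|
| Protocol Tables 9-10 | 1-8, 10-12 | Day 0 and Day 1: "Additional samples collected during D0 and D1 as per Schedule of Events timing" | Day 1 only: "Additional sample collected D1 as per Schedule of Events timing" |
| Protocol Table 11 | 13, 15, 17 | Day 1 only | Day 0 and Day 1 |
| Schedules of Events, Tables 2-4 | 1-2 (Periods 4-5); 3-8, 10-12 (Periods 1-5) | Pre-dose and follow-up visits | Pre-dose, serial Day 0 hours, follow-up visits |
| SAP 8.1 | 1-2, Periods 1-3 | No Day 0 post-dose times | Day 0 times listed |
| SAP 8.1 | 1-2, Periods 4-5 | Day 0 times listed | Day 0 times listed |

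Both footnotes in Tables 9-11 refer the reader to the Schedule of Events. The SAP reproduces Tables 2-4 with the same pattern as the protocol. Tables 1 and 5 were not in the text available to me. The SAP 8.1 blocks for the remaining cohorts are too broken in that text to assign times to columns.

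Both analytes receive a full parameter set. Protocol 10.3 states: "The following PK parameters will be calculated on SEL-037, uricase activity and SEL-110 and assessed". SAP 4.1 has parameters "calculated on SEL-037 and SEL-110 (rapamycin) PK concentration as well as uricase activity separately for each analyte", under an infusion noncompartmental model. In SAP 8.2, Cmax and Tmax "will be read directly from the concentration-time plot". SAP 8 treats serum pegsiticase concentration and uricase activity alike as measures of SEL-037 pharmacokinetics.

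**The concern.** SEL-037 pharmacokinetics is a secondary objective. A one-hour infusion peaks at its end. An analyte first sampled on the next day cannot show that peak, so what is reported as Cmax is a Day 1 level, Tmax is a visit time, and the first segment of the AUC is a straight line up to the Day 1 value.

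These parameters are then used. SAP 8.6 tests Cmax, AUC0-last and AUCtau by ANOVA. SAP 8.7 models the effect of SEL-110 dose on SEL-037 parameters and contrasts Cohorts 13 and 15 with Cohort 11. SAP 10.5 tabulates CL, Cmax, Tmax and AUC by antibody status. The reliability rules in SAP 8.2 flag only lambda-z, half-life, AUCinf, CL and Vd, so nothing there catches a Day 1 Cmax, a schedule-fixed Tmax, AUC0-last or AUCtau.

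**Working it through.** The plan states no figure to reproduce. The check has two parts: what each version implies, and how large the effect could be.

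**Inputs.** In Table 3 the SEL-037 infusion runs from one to two hours after the start of SEL-110 ("Study drug IV (SEL-037) : 60-120 min"). SAP 8.1, under "Time from start of dose for SEL-037, h", places the Day 1 sample at 23 h in Periods 1-3, and later samples at 167, 335, 503 and 671 h. The AUC rule is linear-log trapezoidal (SAP 8.2). The human half-life of SEL-037 is not given; I assume 1 to 14 days, a one-compartment model and a 1 h infusion.

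**Which analyte loses its peak.** Under Tables 9-10 it is uricase activity. Under Tables 2-4 it is SEL-037 concentration. Neither protocol version gives both analytes a Day 0 series.

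**Tmax.** With samples only at 0, 23, 167, 335, 503 and 671 h, the maximum falls at 23 h for every assumed half-life, against a true value of 1 h.

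**Cmax.** With k = ln 2 / half-life, observed/true = C(23)/C(1) = exp(-22k).

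**AUCinf, first dose.** The segment from 0 to 23 h is a straight line from zero, with area 11.5 x C(23); the rest is C(23)/k. Relative to the true area this gives

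ratio = [(1 - exp(-k))/k] x exp(-22k) x (1 + 11.5k).

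At 3 days, k = 0.00963 per hour, so the ratio is 0.9952 x 0.8091 x 1.1107 = 0.894. The overstatement of CL is 1/ratio - 1.

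| Half-life (days) | Cmax observed/true | AUCinf observed/true | CL too high by |
|---|---|---|---|
| 1 | 0.530 | 0.696 | 44% |
| 3 | 0.809 | 0.894 | 12% |
| 7 | 0.913 | 0.955 | 5% |
| 14 | 0.956 | 0.977 | 2% |

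With the Day 0 times restored (0.5, 1, 2, 5 and 8 h), both ratios are 1.0 and Tmax is 1 h throughout. In Periods 4-5 of Part B the Day 1 sample comes 24 h after the start of SEL-037, so the Cmax ratio is exp(-23k), that is 0.515 to 0.954. The Cmax ratio also holds in later periods under this model. The AUC figures apply to the first dose only, because later periods start from residual drug.

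**Does the lambda-z rule remove the extremes?** It needs three quantifiable points excluding Cmax. With Cmax at 23 h, the levels at 167, 335 and 503 h must be measurable. As fractions of peak, exp(-166k), exp(-334k) and exp(-502k), they are:

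- 1-day half-life: 0.8%, about 0.006% and 0.00005%. Three quantifiable points are implausible, though no quantification limit is given, so AUCinf and CL would probably be flagged and excluded.
- 3-day half-life: 20%, 4% and 0.8%. Reporting is plausible.

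The 1-day AUCinf and CL figures are therefore not a fair statement of what would be reported. The rule does not cover Cmax, Tmax, AUC0-last or AUCtau.

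**Contrasts.** If the laboratory tables govern, Cohort 11 (Table 10) has Day 0 SEL-037 concentrations and Cohorts 13 and 15 (Table 11) do not. With identical true pharmacokinetics, the SAP 8.7 contrasts in Periods 4-5 would show Cmax in Cohorts 13 and 15 at 53% to 96% of that in Cohort 11 from sampling alone. The reverse holds for uricase activity. The pooled Part A and Part C analysis in SAP 8.6 (Periods 1-3) has the same mixture.

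**The case against.** The best defence is that a governing schedule exists. Protocol 10.1 points to the laboratory manual and the Schedule of Events, the footnotes themselves defer to it, and Table 11 agrees with Tables 2-4. The simplest explanation is that two superscripts were transposed in Tables 9-10. Table 9 has another odd marker: Total Complement, drawn only at screening, carries the Day 0 and Day 1 footnote there but a different one in Tables 10 and 11. This may well be so, and it would make the sampling in the contrasts alike, subject to Table 5. It does not remove the problem: SEL-037 concentration would then lack a Day 0 peak while Cmax and Tmax are still derived for it.

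The SAP limits parameter derivation to cases where it is possible. It gives no criterion, however, and a maximum can always be read off a sparse profile.

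Several stronger readings do not stand:

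- Table 3, as extracted, could suggest that SEL-037 sampling starts at Day 7. Its columns may have shifted, and both the Day 1 footnote and the 23 h entries in SAP 8.1 contradict that reading.
- A reader might infer that one analyte lacks a peak everywhere. SAP 8.1 lists Day 0 times for both in Cohorts 1-2, Periods 4-5, which agrees with neither protocol version.
- A reader might infer a demonstrated bias in the antibody comparisons. Protocol 4.3.2.1 does link antibodies with faster clearance, and fast clearers lose most when early samples are absent, so a differential effect is plausible. No size can be derived from the documents, and SAP 10.5 makes no inference there.
- A very short typical half-life is also doubtful. The same section reports that the uric acid effect lasted to Day 7 in all but one subject.

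**Conclusion.** The contradiction is real for Cohorts 1-8 and 10-12, and it has a consequence under either protocol version. The analyte without Day 0 samples gets a Tmax fixed by the visit schedule and a Cmax about 4% to 47% too low for assumed half-lives of 14 to 1 days. AUCinf is about 2% to 11% too low at 14 to 3 days, and CL correspondingly about 2% to 12% too high; at shorter half-lives these would probably be excluded. If the half-life is a week or more, the AUC error is about 5% or less and the harm lies mainly in Cmax and Tmax. All sizes rest on the one-compartment model and the assumed half-life.

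The mixed-sampling problem in SAP 8.6 and 8.7 arises only if the laboratory tables govern. It would be too strong to conclude that the secondary objective is lost: under either version one SEL-037 measure keeps its Day 0 profile. The point should be corrected, but it does not undermine the trial.

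**What to change.** - Reconcile the laboratory schedules (Tables 9-11), the Schedules of Events and SAP 8.1 to one sampling schedule per analyte, stated the same way in each place.
- Add to SAP 8.2 that Cmax, Tmax, AUC, CL and Vd, and the comparisons of them in 8.6, 8.7 and 10.5, are reported only for the analyte and profiles with Day 0 post-infusion samples.
- For the other analyte, report Day 1 to Day 28 concentrations or activity descriptively.

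This costs table corrections and a short SAP addition. Assaying both analytes on existing Day 0 serum is an option only if volume and handling permit. The documents do not settle that: handling is left to the laboratory manual, and Part C uric acid samples are split between ambient and frozen storage.
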